8.3.11 Reporting of Serious Adverse Events, Deaths, and Pregnancy

8.3.11.1 Reporting of Serious Adverse Events

Any SAE (see Section 8.3.7) that occurs after signing the study ICF through the Final Visit (ie, End of Study or Early Discontinuation Visit) must be expeditiously reported whether or not considered attributable to the study drug. Each SAE must be fully recorded in the subject's eCRF and SAE Report Form. In addition, any SAE that occurs after the end of study/early discontinuation should be reported if the investigator feels that the event is related to the use of IP.

SAEs will be reported using the designated SAE Report Form. When the investigator becomes aware of an SAE, she/he must submit a completed, signed, and dated SAE Report Form (in English) within 24 hours to the sponsor by email/fax. The date of this SAE discovery by the study center staff should be documented in the source documents (ie, medical records).

Each SAE must be followed up until resolution or stabilization. After the initial report, all relevant information for SAE follow-up, and for the outcome, must also be supplied to the sponsor in a timely manner (within 3 days from its identification or within 24 hours for relevant new information) by means of the SAE Report Form. In addition, the sponsor or contract research organization may request additional information and/or reports.

All SAE Report Forms must be reported to:

When required, and according to local law and regulations, SAEs must be reported to the IRB/EC and regulatory authorities. Copies of the investigator's reports must be sent to the sponsor.

8.3.11.2 Reporting of Deaths

The following considerations should be made for all deaths occurring during the clinical study:

- Any death that is unequivocally due to disease progression should not be reported as an SAE, but should be documented in the eCRF as well as in the subject's medical record.
- Any death that is not unequivocally due to disease progression should be immediately reported as an SAE (see Section 8.3.11.1) as well as documented in the subject's medical record. Every effort should be made to establish a cause of death. Reporting of the SAE should include a comment regarding the co-involvement of progression of disease, if appropriate, and should assign a single primary cause of death (AE) together with any contributing causes.

8.3.11.3 Reporting Pregnancy

While pregnancy itself is not a true "AE," pregnancy occurring in a clinical study must be followed to collect information regarding the experiences of gestation and pregnancy. The investigator must report any pregnancy that occurs in a study subject or partner of a male subject from the first treatment exposure until 28 days after the last dose of treatment. A pregnancy will not be considered an AE unless a relation to the treatment is suspected. A Pregnancy Report Form must be completed and sent as soon as possible to the sponsor. A copy of the form should be filed at the study center for pregnancy follow-up until delivery or to the end of pregnancy. Any anomalies, complications, abnormal outcomes, or birth defect observed in the child must be reported as an SAE within 24 hours of the investigator or study personnel's first knowledge.

Please use the email address or fax numbers (back up only) in Section 8.3.11.1 for reporting pregnancy.

8.4 Type and Duration of the Follow-Up of Subjects after Adverse Events

In so far as is possible, all individuals will be followed up until the AE or suspected ADR has been resolved. If an AE/suspected ADR/SAE is present when the subject has completed the study, the course of the event must be followed until the final outcome is known, or the event has been stabilized and no further change is expected and the investigator decides that no further follow-up is necessary.

9 STATISTICS

9.1 Statistical Methods

Unless otherwise specified, descriptive statistics will include the number of non-missing observations, mean, standard deviation (SD), median, minimum and maximum values for the continuous/quantitative data or absolute and relative frequency counts and percentages for categorical/qualitative data.

Data handling and evaluation procedures will be described in the Statistical Analysis Plan (SAP).

9.1.1 Demographic and Baseline Characteristics

Demographic and baseline characteristics will be summarized by treatment group. For quantitative variables, mean, SD, median, minimum, and maximum will be provided. For qualitative variables, the frequency and percentage will be provided.

9.1.2 Efficacy Analysis

9.1.2.1 Primary Endpoint

This is a study to demonstrate superiority of SMT + Albutein 20% to SMT alone on 1-year transplant-free survival. The null hypothesis is that the hazard functions for liver transplantation or death are the same for the 2 treatment groups, or equivalently, the hazard ratio is equal to 1. The alternative hypothesis is that the hazard functions for liver transplantation or death are not the same for the 2 treatment groups, or equivalently, the hazard ratio is not equal to 1. The effect of SMT + Albutein 20% administration on the transplant-free survival at 1 year after randomization versus SMT alone will be summarized by means of Kaplan-Meier survival estimates and curves and compared between treatment groups by means of the Log-rank test stratified by region (Europe or NA) and history of hospitalization for acute decompensation of liver cirrhosis (yes or no). An un-stratified analysis will be performed as a sensitivity analysis.

In the event that clinically and statistically significant imbalances are observed between treatment groups in any of subjects' baseline characteristics, sensitivity analyses will be performed in which treatment effects will be adjusted by those characteristics by fitting an appropriate Cox Proportional-Hazards (PH) model. In addition, subgroup analyses by age group, sex, race, region (Europe vs NA), and history of hospitalization for acute decompensation of liver cirrhosis (yes vs no) will be carried out for the primary endpoint.

The primary efficacy analysis will be carried out on the ITT population and repeated on the Per-Protocol (PP) population (see Section 9.7 for description of subject populations for analysis).

9.1.2.2 Secondary Endpoints

The analysis of the secondary endpoints will be performed using the ITT population.

The effects of SMT + Albutein 20% administration on the overall survival at 3, 6, and 12 months and transplant-free survival at 3 and 6 months after randomization versus SMT alone will be assessed by carrying out the same analyses for the primary efficacy variable described above.

Total number of paracenteses and incidence of refractory ascites will be listed for each subject, summarized by treatment group, and compared between treatment groups by means of analysis of covariance (ANCOVA) or Student's t test (for normally-distributed variables),

Poisson regression model (for count variables), and Fisher's exact test or Chi-square test (for binomial variables).

The fixed-sequence testing method will be used to adjust for multiplicity in the analyses of the secondary efficacy endpoints. Specifically, the superiority of SMT + Albutein 20% versus SMT alone for the secondary efficacy endpoints will only be tested if the superiority for the primary efficacy endpoint is demonstrated at the 2-sided significance level of 5%. For the secondary efficacy endpoints, each subsequent hypothesis is tested only if the superiority for the previous comparison(s) has been demonstrated at a 2-sided significance level of 5%. The order in which the null hypotheses will be tested is predetermined for the secondary efficacy endpoints as follows:

- 1. Time to death through 1 year after randomization
- 2. Time to liver transplantation or death through 6 months after randomization
- 3. Time to death through 6 months after randomization
- 4. Time to liver transplantation or death through 3 months after randomization
- 5. Time to death through 3 months after randomization
- 6. Total number of paracenteses
- 7. Incidence of refractory ascites according the ICA criteria

9.1.2.3 Exploratory Endpoints

As appropriate to the data, the original values or changes from baseline (last measurement taken prior to the start of study treatment on Day 1) of the following exploratory endpoints will be listed for each subject, summarized by treatment group, and compared between treatment groups by means of ANCOVA or Student's t tests (for normally-distributed variables), non-parametric Mann-Whitney U test (for non-parametric variables), Kaplan-Meier estimates and Log-rank test (for time-to-event variables), Poisson regression model (for count variables), and Fisher's exact test or Chi-square test (for binomial variables):

Incidence of ACLF, CLIF-C OF score, CLIF-C ACLF score, CLIF-C AD score, MELD score, Child Pugh score, number and length of hospital readmission for an acute complication of cirrhosis, number and length of ICU admission, incidence of disease-related complications, serum albumin concentration, albumin functional capacity (albumin binding capacity), incidence of insertion of TIPS for refractory ascites, and the EQ-5D-5L health questionnaire.

For the normally-distributed variables, the ANCOVA model will include change from baseline as the dependent variable, treatment as a fixed factor, and baseline value as a covariate. If any potential confounders are identified among subjects' baseline characteristics, they will be included as additional covariates in the ANCOVA models to adjust treatment effects. In addition, for the longitudinal measurements taken repeatedly over time, the treatment effects may be explored by using the mixed-effect model repeated measures analysis.

9.1.3 Safety Analysis

The safety analyses will be addressed by listing and tabulation of AEs (including suspected ADRs), vital signs, physical assessments, and clinical laboratory tests. Data will be described using descriptive analyses and treatment comparisons will be based on review of descriptive statistics. The safety analyses will be based on the Safety population.

9.1.3.1 Adverse Events

Adverse events will be coded and classified using MedDRA[®] terms (system organ class and preferred terms).

When a causal relationship of an AE is classified by the investigator as definitively or possibly related, the event will be defined as a suspected ADR. A suspected ADR with a causal relationship of "definitively related" will be defined as an AR. The sponsor will consider the investigator's causality assessment and also provide its own assessment. If there is any disagreement in the causality assessment between the investigator and the sponsor, a separate summary of suspected ADRs/ARs will be provided.

For summary purpose, AEs will be classified as treatment-emergent AEs (TEAEs) or non-TEAEs depending on the comparison of AE onset date/time with the start date/time of study treatment. A TEAE will be defined as an AE which occurs between the start of study treatment and the final visit of the clinical study. A non-TEAE will be defined as an AE which occurs prior to the start of study treatment. Non-TEAEs and TEAEs will be summarized separately.

In addition, TEAEs, including suspected ADRs, will be summarized by each treatment group, system organ class, preferred term, causal relationship, severity, and seriousness (serious versus non-serious) using descriptive statistics. At each level of summarization, a subject will only be counted once per system organ class or preferred term using the most severe AE or the AE with the strongest causal relationship to the treatment.

AEs temporally associated with the infusion of the IP (ie, infusional AEs, including infusional suspected ADRs) will be summarized by presenting infusion/subject incidences and percentages and listed.

Subjects with SAEs, AEs leading to death, or who withdraw from the study because of an AE will also be individually listed and summarized.

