8.3.3 Adverse Event Definitions

8.3.3.1 Adverse Events

An AE is defined as any untoward medical occurrence in a subject or clinical investigation subject administered a medicinal product or study treatment and which does not necessarily have a causal relationship with this administration. An AE can therefore be any unfavorable and unintended sign (including any abnormal laboratory finding, for example), symptom, or disease temporally associated with the use of a medicinal product, whether or not considered related to the medicinal product. This includes worsening of a pre-existing condition or increase in frequency of a pre-existing condition.

An AE is also defined as any occurrence that is new in onset, expected, or aggravated in severity or frequency from a baseline condition, or abnormal results or diagnostic procedures including laboratory test abnormalities.

In this clinical study, deterioration of the targeted disease and symptoms associated with the targeted disease will not be considered an AE as long as the deterioriation is anticipated and there is no evidence suggesting a causal relationship between the study drug and the AE. Anticipated disease progression includes, but not limited to: HE, GI bleeding, portal hypertension, ascites, SBP, hyponatremia and HRS (see Section 8.3.10).

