8.3.8 Adverse Event Documentation

All AEs and SAEs occurring after the subject has **signed the ICF through the Final Visit** (ie, End of Study or Early Discontinuation Visit) must be fully recorded in the subject's eCRF and SAE form (if serious) as well as in the medical record. If no AE has occurred during the study period, this should also be indicated in the eCRF.

It is the responsibility of the investigator to ensure that AEs are appropriately recorded.

At each visit, AEs will be elicited by asking the individual a non-leading question such as "Do you feel different in any way since the last visit?" Moreover, AEs will also be collected through directly observed events or spontaneously volunteered by the subject. Clearly related signs, symptoms, and abnormal diagnostic procedures should preferably be grouped together and recorded as a single diagnosis or syndrome wherever possible.

The following variables must be recorded in the AE eCRF:

- The verbatim term (a diagnosis is preferred)
- Date/time of onset
- Date/time of resolution
- Severity (mild, moderate, severe)
- Causality (unrelated/not related, possibly related, definitely related)*
- Seriousness (yes, no)
- Action taken (with regard to IP)
- Other action (to treat the event)
- Outcome and sequel (follow-up on AE)

* An AE occurring before subject's exposure to treatment will be labeled as "unrelated/not related".

If it is a preexisting AE that gets worse regarding intensity or frequency, it should be indicated.

For AEs that occur during infusions, the infusion rate in effect at the time of onset of the AE (if applicable), the time of onset of the AE and the time of AE change materially in intensity and/or resolve will be captured in the eCRF.

In addition to the investigator's own description of the AEs, each AE will be encoded according to the Medical Dictionary for Regulatory Activities (MedDRA).

For example, a laboratory test abnormality considered clinically significant, eg, causing the subject to withdraw from the study, requiring treatment or causing apparent clinical manifestations, or judged clinically significant in the context of the subject's medical history by the investigator, should be reported as an AE. Each event must be described in detail along with start and stop dates, severity, relationship to treatment, action taken, and outcome. Each event must be adequately supported by documentation as it appears in the subject's medical or case file.

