6.1.6 Adverse Events

Adverse events will be classified as TEAEs or non-Treatment-Emergent AEs (non-TEAEs), based on the comparison of the AE onset date/time with the start date/time of study treatment. For the SMT + Albutein 20% treatment group, TEAE is defined as an AE occurring during or after the first Albutein dose administration. For the SMT treatment group, it is assumed that subjects were already receiving SMT per institutional standards at the time of randomization; therefore, a TEAE will be defined as an AE occurring at or after randomization.

A non-TEAE will be defined as an AE which starts during screening and prior to the start of the first administration of study treatment in the SMT + Albutein 20% treatment group. For the SMT group, a non-TEAE is an AE that starts during screening and prior to randomization.

An AE with incomplete start date/time will be determined to be a TEAE or non-TEAE using the conservative rule specified in [Appendix 2](#).

Any AE with a missing end date will be considered ongoing.

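### Treatment emergence is set by onset date alone, and nothing requires post-dose worsening of an adverse event that began before the first dose to be recorded as a new, treatment-emergent event

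*Protocol*

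**What the plan says.** **Classification.** Protocol 9.1.3.1 sorts AEs into TEAEs and non-TEAEs "depending on the comparison of AE onset date/time with the start date/time of study treatment". It continues: "A TEAE will be defined as an AE which occurs between the start of study treatment and the final visit of the clinical study", and "A non-TEAE will be defined as an AE which occurs prior to the start of study treatment". SAP 6.1.6 classifies in the same way, "based on the comparison of the AE onset date/time with the start date/time of study treatment", and for the Albutein arm states: "A non-TEAE will be defined as an AE which starts during screening and prior to the start of the first administration of study treatment". For the SMT arm the SAP uses randomization as the dividing point. SAP Appendix 2, which handles incomplete dates, works only from AE start and end dates. SAP section 12 explains a deliberate change to the TEAE definition, made to avoid bias between arms, and adds nothing on worsening.

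**Recording.** Protocol 8.2.1 collects AEs from consent. Protocol 8.3.8 says of worsening: "If it is a preexisting AE that gets worse regarding intensity or frequency, it should be indicated". The same section says that an AE before the subject's "exposure to treatment will be labeled as" unrelated or not related.

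**AE definition.** Protocol 8.3.3.1 defines an AE broadly: "This includes worsening of a pre-existing condition or increase in frequency of a pre-existing condition".

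**Use.** Suspected ADRs, meaning AEs rated possibly or definitely related, are the main safety variable (Protocol 8.1). SAP 5.4.2 assigns ADR causality to Albutein only.

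**The concern.** The AE definition recognises worsening, but the rule that decides which AEs reach the TEAE tables does not. Between the two, 8.3.8 does not say whether worsening becomes a new record or a note on the old one. Two sites could therefore record the same clinical course differently, and the tables would count one and not the other.

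This matters because subjects are screened in hospital during acute decompensation, so some will have an open AE at the first infusion. Protocol 2.3 lists heart failure and pulmonary edema among the product's most serious reactions, and worsening of a sign already present is a plausible way for such a reaction to begin. Because suspected ADRs are attributed to Albutein only, any that are lost in this way lower the count in that arm alone.

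**Working it through.** The plan gives no figure on this point, so the check is to follow one event through the rules. Take an AE that starts after consent and before the first infusion, is mild, and becomes severe after the infusion. The documents leave two routes open.

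| Step | Route A: worsening noted on the existing record | Route B: worsening entered as a new AE |
|---|---|---|
| Basis | Protocol 8.3.8, note the worsening | Protocol 8.3.3.1, worsening is itself an AE |
| Onset used | Before first dose | After first dose |
| TEAE (Protocol 9.1.3.1, SAP 6.1.6) | No | Yes |
| Causality | Unrelated, fixed by 8.3.8 | Open to rating |
| Suspected ADR | No | Possible |
| Infusional summary (SAP 10.1) | No | Yes, if within the window |
| Tabulated by severity or causality (SAP 10.1) | No; prior-onset AEs appear by SOC and preferred term only | Yes |
| Listing of all AEs (SAP 10.1) | Yes, flagged as not treatment-emergent | Yes |

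The infusional row needs a word. SAP 10.1 measures the 72 hours from infusion end to AE start, and the summary is of temporally associated TEAEs. A record with a pre-dose start fails both conditions.

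No passage chooses between A and B. The wording of 8.3.8 leans towards A: it speaks of a preexisting AE getting worse, and its list of required variables has one onset, one severity and one causality per AE, with no general date of worsening. It does capture the time of a material change in intensity, but only for AEs that occur during infusions.

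**Scope.** Only AEs that start between consent and first dose are exposed. Under the current protocol, randomization falls within 72 hours of screening with the first dose on the same day. SAP section 12 notes that earlier protocol versions allowed longer. A condition present before consent that worsens after dosing is an AE under 8.3.3.1 with a post-dose onset, and so is outside the problem.

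**Size.** The documents give no rates. As an illustration only, assume that 10–20% of the planned 205 Albutein subjects have an AE starting in this window and that 10–25% of those worsen afterwards:

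- low: 205 × 0.10 × 0.10 = 2.05, about 2 subjects (1%)
- high: 205 × 0.20 × 0.25 = 10.25, about 10 subjects (5%)

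Both percentages are assumptions. The result counts worsening from any cause and supposes that every site takes route A, so under these inputs it is a ceiling on the loss and not an estimate of missed drug reactions.

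**The case against.** The strongest reply is that the protocol already supplies the answer. Under 8.3.3.1, aggravation after the first infusion is an AE in its own right. It then has a post-dose onset, is a TEAE under both definitions, and can be rated related. The unrelated label in 8.3.8 covers AEs that occur before exposure, not their later aggravation. No passage tells sites to keep worsening on the existing record.

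There are also other channels:

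- Laboratory abnormalities that worsen to a medically significant degree after treatment starts become AEs (Protocol 8.2.3).
- A clinically significant vital-sign abnormality during an infusion is reported as an infusional AE (Protocol 9.1.3.3).
- A sign that progresses to a new diagnosis, such as pulmonary edema, can be a new AE, since 8.3.8 prefers diagnoses.
- SAEs are reported from consent (Protocol 8.3.11.1), and the sponsor makes its own causality assessment (8.3.4).

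Most of this stands. A reader might infer from the onset-only rule that post-dose worsening can never reach the TEAE tables and must be called unrelated. The documents do not support that, because route B is open and the label is limited to pre-exposure events. What remains is that route B is permitted, not required. The other channels are also partial. They do not cover symptoms, such as dyspnea, that worsen without a new diagnosis or a flagged measurement. The SAP's serious-event tables are of treatment-emergent SAEs, and SAP 10.1 defines suspected ADRs by the investigator's rating.

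**Conclusion.** The point holds as a gap in the rules, not as a bar. TEAE status depends on onset alone, and the recording instruction leaves the site to decide whether worsening gets its own onset. Where the site annotates the pre-dose record, real post-dose worsening is absent from the TEAE, suspected-ADR and infusional summaries and survives only in the listing.

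The number affected cannot be derived from the documents and is probably small: the window is short, some sites will open new records, and other provisions catch part of the rest. The documents also give no expected number of suspected ADRs, so they do not support a claim that the loss would be a large share of that count. The conclusion rests on the text of the two documents; eCRF completion guidelines, which are not among them, could already settle the matter. Because the main safety variable is involved and the remedy is cheap, the change is worth making.

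**What to change.** 1. In Protocol 9.1.3.1, SAP 6.1.6 and SAP Appendix 2, state that an AE starting before treatment (before randomization for SMT) that worsens in intensity, seriousness or frequency afterwards is a TEAE.
2. In Protocol 8.3.8, require the worsening to be entered as a new AE record, with the date and time of worsening as its onset and its own severity, seriousness and causality.
3. In the same section, limit the automatic unrelated label to the pre-exposure record.

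A worsening indicator on the existing record would not be enough. No general worsening date is collected, so the indicator cannot show that the change followed the first dose, and the infusional window in SAP 10.1 would still be counted to the pre-dose start. For records already completed under the present wording, pre-dose AEs marked as worsened can be queried before database lock.

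The cost is protocol and SAP wording, an eCRF completion instruction, and slightly more TEAEs in both arms, since the same rule applies to each.
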